5.3. Other Considerations for Data Analyses and Data Handling Conventions

Other considerations for data analyses and data handling conventions are outlined in the appendices:

Section	Component
10.2	Appendix 2: Study Phases and Treatment Emergent Adverse Events
10.3	Appendix 3: Data Display Standards & Handling Conventions
10.4	Appendix 4: Derived and Transformed Data
10.5	Appendix 5: Reporting Standards for Missing Data
10.6	Appendix 6: Division of AIDS (DAIDS) Table for Grading the Severity of Adult and Pediatric Adverse Events
10.7	Appendix 7: Values of Potential Importance

6. STUDY POPULATION ANALYSES

6.1. Overview of Planned Study Population Analyses

The study population analyses will be based on the "Safety" population, unless otherwise specified.

Study population analyses including analyses of participant's disposition, protocol deviations (including inclusion/exclusion criteria deviations), demographic and baseline characteristics, prior and concomitant medications, and exposure will be based on GSK Core Data Standards. Details of the planned displays are presented in Appendix 9: List of Data Displays.

7. PHARMACOKINETIC ANALYSES

7.1. Primary Pharmacokinetic Analyses

7.1.1. Endpoint / Variables

7.1.1.1. Drug Concentration Measures

Refer to Appendix 3: Data Display Standards & Handling Conventions (Section 10.3.3 Reporting Standards for Pharmacokinetics). Plasma concentrations of DTG and GSK3640254 will be measured and reported.

7.1.1.2. Derived Pharmacokinetic Parameters

Pharmacokinetic parameters will be calculated by standard non-compartmental analysis according to current working practices and using the currently supported version of WinNonlin (6.4 or higher). All calculations of non-compartmental parameters will be based on actual sampling times. Pharmacokinetic parameters listed will be determined from the plasma concentration-time data, as data permits.

Parameter	Parameter Description
Cmax	Maximum observed concentration, determined directly from the concentration-time data.
Ст	Plasma concentration at the end of the dosing interval
AUC(0-T)	Area under the plasma concentration-time curve from time 0 to the end of the dosing
	interval at steady state, to be calculated using the linear trapezoidal rule for each
	incremental trapezoid and the log trapezoidal rule for each decremental trapezoid.

NOTES:

Additional parameters may be included as required.

7.1.2. Summary Measure

Area under concentration-time curve [AUC(0- τ)], C τ , and Cmax at steady state following doses of DTG 50 mg QD Days 1 through 5 in Period 1, GSK3640254 200 mg QD Days 1 through 7 in Period 2, and DTG 50 mg QD coadministered with GSK3640254 200 mg QD on Days 1 through 7 in Period 3 in healthy participants.

7.1.3. Population of Interest

The primary PK analyses will be based on the PK concentration population for plasma PK concentrations and the PK parameter population for plasma PK parameters and statistical analysis.

7.1.4. Statistical Analyses / Methods

Details of the planned displays are provided in Appendix 9: List of Data Displays and will be based on GSK Data Standards and statistical principles.

Unless otherwise specified, endpoints / variables defined in Section 7.1.1 will be summarised using descriptive statistics, graphically presented (where appropriate), and listed.

7.1.4.1. Statistical Methodology Specification

The following PK statistical analyses will only be performed if sufficient data is available (i.e. if participants have well defined plasma profiles).

Endpoint / Variables

• Plasma primary PK endpoints include AUC(0-τ), Cτ, and Cmax, as data permit

Model Specification

- Analyses will be performed on the natural logarithms of AUC(0-τ), Cτ, and Cmax using linear mixed-effect models with period as a fixed effect, participants as random effect, and measurements within participant as repeated measures.
- Effects will be estimated, and CIs will be constructed for the following treatment comparisons: Period 3 versus Period 1 (DTG)
 - Period 3 versus Period 2 (GSK3640254)
- Point estimates and 90% CIs for treatment differences on the log scale derived from the model will be exponentiated to obtain estimates for geometric mean ratios and CIs on the original scale.

Model Checking & Diagnostics

Based on the data.

Model Results Presentation

 Statistical analysis by analysis of variance (ANOVA) will be presented in tabular format with geometric mean ratios for:

Period 3 versus Period 1 (DTG)

Period 3 versus Period 2 (GSK3640254)

7.2. Secondary Pharmacokinetic Analyses

7.2.1. Endpoint / Variables

7.2.1.1. Drug Concentration Measures

Refer to Appendix 3: Data Display Standards & Handling Conventions (Section 10.3.3 Reporting Standards for Pharmacokinetics)

7.2.1.2. Derived Pharmacokinetic Parameters

Pharmacokinetic parameters will be calculated by standard non-compartmental analysis according to current working practices and using the currently supported version of WinNonlin (6.4 or higher). All calculations of non-compartmental parameters will be based on actual sampling times.

Plasma PK parameters listed below will be determined from the total plasma concentration-time data, as data permits.

Parameter	Parameter Description
Tmax	Time to first occurrence of Cmax
t½	Terminal half-life will be calculated as: $t\frac{1}{2} = \ln 2 / \lambda z$
λz	Terminal-phase rate constant

NOTES:

Additional parameters may be included as required.

7.2.2. Summary Measure

Tmax and t1/2 at steady state following doses of DTG 50 mg QD Days 1 through 5 in Period 1, GSK3640254 200 mg QD Days 1 through 7 in Period 2, and DTG 50 mg QD coadministered with GSK3640254 200 mg QD on Days 1 through 7 in Period 3 in healthy participants.

7.2.3. Population of Interest

The secondary PK analyses will be based on the PK concentration population for plasma PK concentrations, and the PK parameter population for plasma and statistical analysis, unless otherwise specified.

7.2.4. Statistical Analyses / Methods

Details of the planned displays are provided in Appendix 9: List of Data Displays and will be based on GSK Data Standards and statistical principles.

Unless otherwise specified, endpoints / variables defined in Section 7.2.1 will be summarised using descriptive statistics, graphically presented (where appropriate) and listed.

Secondary plasma PK parameters (Tmax and t1/2) will be estimated for DTG (Periods 1 and 3) and GSK3640254 (Periods 2 and 3). Summary statistics (arithmetic mean, geometric mean, median, standard deviation (SD), minimum, maximum, and coefficient of variation) for plasma GSK3640254 and DTG PK parameter values will be summarized by treatment.

Predose (trough) PK plasma concentrations (DTG: Days 2 through 5 of Period 1 and Days 2 through 7 of Period 3; GSK3640254: Days 4 through 7 of both Period 2 and Period 3) will be summarized using the PK Parameter Population and used to assess achievement of steady state.

8. SAFETY ANALYSES

The safety analyses will be based on the "Safety" population, unless otherwise specified.

8.1. Adverse Events Analyses

Adverse events analyses including the analysis of AEs, SAEs and other significant AEs will be based on GSK Core Data Standards. The details of the planned displays are provided in Appendix 9: List of Data Displays.

8.2. Clinical Laboratory Analyses

Laboratory evaluations including the analyses of chemistry laboratory tests, hematology laboratory tests, urinalysis, and liver function tests will be based on GSK Core Data Standards and will be graded using the Division of AIDS (DAIDS) Table for Grading the Severity of Adult and Pediatric Adverse Events (Version 2.1, July 2017). The details of the planned displays are in Appendix 9: List of Data Displays.

8.3. Other Safety Analyses

The analyses of non-laboratory safety test results including ECGs, vital signs, and Columbia Suicide Severity Rating Scale (C-SSRS) will be based on GSK Core Data Standards, unless otherwise specified. A figure of mean change from baseline in QTcF interval along with the 2-sided 95% CI using Student's t distribution will be presented by treatment and visit. The details of the planned displays are presented in Appendix 9: List of Data Displays.

10. APPENDICES

10.1. Appendix 1: Schedule of Activities

10.1.1. Protocol Defined Schedule of Events

Screening Visit

Procedure	Screening (up to 28 days before Day 1)
Outpatient visit	Х
Informed consent	X
Inclusion and exclusion criteria	X
Demography	X
Full physical examination including height and weight ¹	X
Laboratory assessments (hematology, chemistry, urinalysis)	X
12-lead electrocardiogram	X
Vital sign measurements	X
Medication/drug/alcohol history	Х
Past and current medical conditions	Х
Columbia Suicide Severity Rating Scale	Х
Serum pregnancy test	X
Follicle-stimulating hormone (as needed, to confirm postmenopausal status)	Χ
Drug, alcohol, and cotinine screen	Χ
HIV, Hepatitis B and C screening	Х

HIV = human immunodeficiency virus.

¹ A full physical examination will include at a minimum, assessments of the skin, cardiovascular, respiratory, gastrointestinal, and neurological systems.

Time and Events Table

	Peri	od 1	W	P	Period 2	2			ſ	Period 3	3				Follo	w-up		Notes
Procedure	Day -1	Day 1-5	Day 6-9	Day 1-5	Day 6	Day 7	Day 1	Day 2	Day 3	Day 4	Day 5	Day 6	Day 7	Day 8	Day 9	Day 10 ¹	Day 11	
Admit to clinic	Χ																	
Discharge from clinic																	Χ	
Brief physical examination	Х															Х		A brief physical examination will include, at a minimum, assessments of the skin, lungs, cardiovascular system, and abdomen (liver and spleen).
Vital sign measurements	Х	Х		Х	Х	Х	Х	Х	Х	Х	Х	Х	Х	Х	Х	Х	Х	
12-Lead ECG	х	D1 and D5		D1 and D5			Х			Х	Х		Х			х		All ECGs in Period 1-3 will be pre-dose, post-dose at 2 hours, and post-dose at 4 hours. The predose ECGs on Day 1 of both Period 1 and Period 2 will be taken in triplicate.
Drug, alcohol, and cotinine screen	Χ																	See Protocol Appendix 2 for specific tests to be performed.
Laboratory assessments (hematology, chemistry, urinalysis)	Х		D9			Х				Х			Х			Х		See Protocol Appendix 2 for specific tests to be performed.
Pregnancy test	Х															Х		
Columbia Suicide Severity Rating Scale				D1									Х					
Genetic sample	Х																	

	Peri	od 1	W	F	Period 2	!			I	Period :	3				Follo	w-up		Notes
Procedure	Day -1	Day 1-5	Day 6-9	Day 1-5	Day 6	Day 7	Day 1	Day 2	Day 3	Day 4	Day 5	Day 6	Day 7	Day 8	Day 9	Day 10 ¹	Day 11	
Study intervention: Dolutegravir 50 mg		Х					Χ	Χ	Χ	Χ	Χ	Χ	Χ					
Study intervention: GSK3640254 200 mg				Х	Х	Х	Х	Х	Х	Х	Х	Х	Х					
DTG trough PK sampling		D2-4						Х	Х	Х	Х	Х						Blood collection for DTG trough PK samples will be collected on Days 2 through 4 in Period 1, Days 2 through 6 in Period 3.
DTG serial PK sampling		D5	D6-8										Х	х	х	х		Blood collection for PK analysis of DTG will be collected predose, and after dosing at 1, 1.5, 2, 3, 3.5, 4, 4.5, 5, 6, 8, 12, 24, 48, and 72 hours relative to Day 5 dosing in Period 1, and relative to Day 7 dosing in Period 3.
GSK3640254 trough PK sampling				D 4-5	х					Х	Х	х						Blood collection for GSK3640254 trough PK samples will be collected on, Days 4 through 6 in Period 2; and Days 4 through 6 in Period 3.

	Peri	od 1	W	Р	eriod 2				F	Period :	3				Follo	w-up		Notes
Procedure	Day -1	Day 1-5	Day 6-9	Day 1-5	Day 6	Day 7	Day 1	Day 2	Day 3	Day 4	Day 5	Day 6	Day 7	Day 8	Day 9	Day 10 ¹	Day 11	
GSK3640254 serial PK sampling						Х	Х						Х	X	X	X	X	Relative to Day 7 dosing in Period 2, blood for PK analysis of GSK3640254 will be collected predose, and after dosing at 1, 2, 2.5, 3, 3.5, 4, 4.5, 5, 6, 8, 12, and 24 hours. Relative to Day 7 dosing in Period 3, the PK samples will be collected at predose, and after dosing at 1, 2, 2.5, 3, 3.5, 4, 4.5, 5, 6, 8, 12, 24, 48, 72, and 96 hours.
AE review												==→						
SAE review	←									==>								
Concomitant medication review	ew							=>										

AE = adverse event; D = Day; DTG = dolutegravir; ECG = electrocardiogram; PK = pharmacokinetic; SAE = serious adverse event; W = washout.

1 Evaluations scheduled for Day 10 in Period 3 will also be performed for participants who discontinue early.

10.2. Appendix 2: Study Phases and Treatment Emergent Adverse Events

10.2.1. Study Phases

Assessments and events will be classified according to the time of occurrence relative to study treatment start date(/time) and stop date(/time).

Study Phase	Definition
Pre-Treatment	Date and Time ≤ Study Treatment Start Date and Time
On-Treatment	Study Treatment Start Date and Time < Date and Time ≤ Study Treatment Stop Date and Time + 5 days
Post-Treatment	Date and Time > Study Treatment Stop Date and Time + 5 days

10.2.1.1. Study Phases for Concomitant Medication

Study Phase	Definition
Prior	If medication end date is not missing and is before Day -1 of Period 1
Concomitant	Any medication that is not a prior

NOTES:

 Please refer to Appendix 5: Reporting Standards for Missing Data for handling of missing and partial dates for concomitant medication. Use the rules in this table if concomitant medication date is completely missing.

10.2.2. Treatment Emergent Flag for Adverse Events

Flag	Definition
Treatment Emergent	 If AE onset date and time is on or after treatment start date and time & on or before treatment stop date and time + 5 days. Study Treatment Start Date and Time ≤ AE Start Date and Time ≤ Study Treatment Stop Date and Time + 5 days. If the AE onset date is completely missing, the AE is considered as treatment emergent.

NOTES:

- If the study treatment stop date is missing, then the AE will be considered to be On-Treatment.
- Please refer to Appendix 5: Reporting Standards for Missing Data for handling of missing and partial dates for adverse events. Use the rules in this table if the adverse event onset date is completely missing.

10.3. Appendix 3: Data Display Standards & Handling Conventions

10.3.1. Reporting Process

Software	Software							
• The currently supported versions of SAS software (9.4 or higher) will be used.								
Reporting Area	Reporting Area							
HARP Server	\\us1salx00259.corpnet2.com							
HARP Compound	HARP Compound \gsk3640254\mid209712\final_01							
Analysis Datasets	Analysis Datasets							

Analysis datasets will be created according to CDISC standards (SDTM IG Version 3.2 & ADaM IG Version 1.0).

 For creation of ADaM datasets (ADC1/ADCM/ADAE), the same version of dictionary datasets will be implemented for conversion from SI to SDTM.

Generation of RTF Files

RTF files will be generated for all reporting efforts described in the RAP.

10.3.2. Reporting Standards

General

- The current GSK Integrated Data Standards Library (IDSL) will be applied for reporting, unless otherwise stated (IDSL Standards Location: https://spope.gsk.com/sites/IDSLLibrary/SitePages/Home.aspx):
 - 4.03 to 4.23: General Principles
 - 5.01 to 5.08: Principles Related to Data Listings
 - 6.01 to 6.11: Principles Related to Summary Tables
 - 7.01 to 7.13: Principles Related to Graphics
- Do not include participant level listings in the main body of the GSK Clinical Study Report. All participant level listings should be located in the modular appendices as ICH or non-ICH listings.

Formats

- All data will be reported according to the actual treatment the participant received unless otherwise stated.
- GSK IDSL Statistical Principles (5.03 & 6.06.3) for decimal places (DP's) will be adopted for reporting of data based on the raw data collected, unless otherwise stated.
- Numeric data will be reported at the precision collected on the eCRF.
- The reported precision from non eCRF sources will follow the IDSL statistical principles but may be adjusted to a clinically interpretable number of DP's.

Planned and Actual Time

- Reporting for tables, figures, and formal statistical analyses:
 - Planned time relative to dosing will be used in figures, summaries, statistical analyses and calculation of any derived parameters, unless otherwise stated.
 - The impact of any major deviation from the planned assessment times and/or scheduled visit days
 on the analyses and interpretation of the results will be assessed as appropriate.
- Reporting for Data Listings:
 - Planned and actual time relative to study drug dosing will be shown in listings (Refer to IDSL Statistical Principle 5.05.1).
 - Unscheduled or unplanned readings will be presented within the participant's listings.

 Visits outside the protocol defined time-windows (i.e. recorded as protocol deviations) will be included in listings but omitted from figures (mean figures only for PK concentrations), summaries and statistical analyses (excluding statistical analyses of PK parameters).

Unscheduled Visits

- Unscheduled visits will not be included in summary tables except for determining the worst-case values.
- Unscheduled visits will not be included in figures.
- All unscheduled visits will be included in listings.

Descriptive Summary Statistics							
Continuous Data Refer to IDSL Statistical Principle 6.06.1							
Categorical Data	Categorical Data N, n, frequency, %						
Graphical Displays							
Refer to IDSL Statistical Principals 7.01 to 7.13.							

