1.2. Schema

A summary of the overall study design is presented in [Figure 1](#).

Figure 1 Study Design Schematic**1.3. Schedule of Activities (SoA)**

- Screening procedures may be done over more than 1 visit but must all be completed within 28 days prior to the first dose of study intervention.
- The following demographic parameters will be captured: year of birth, sex, race, and ethnicity.
- Medical/medication/family history will be assessed as related to the inclusion/exclusion criteria.

Screening Visit

Procedure	Screening (up to 28 days before Day 1)
Outpatient visit	X
Informed consent	X
Inclusion and exclusion criteria	X
Demography	X
Full physical examination including height and weight ¹	X
Laboratory assessments (hematology, chemistry, urinalysis)	X
12-lead electrocardiogram	X
Vital sign measurements	X
Medication/drug/alcohol history	X
Past and current medical conditions	X
Columbia Suicide Severity Rating Scale	X
Serum pregnancy test	X
Follicle-stimulating hormone (as needed, to confirm postmenopausal status)	X
Drug, alcohol, and cotinine screen	X
HIV, Hepatitis B and C screening	X

HIV = human immunodeficiency virus.

1 A full physical examination will include at a minimum, assessments of the skin, cardiovascular, respiratory, gastrointestinal, and neurological systems.

Procedure	Period 1		W	Period 2			Period 3							Follow-up				Notes	
	Day -1	Day 1-5	Day 6-9	Day 1-5	Day 6	Day 7	Day 1	Day 2	Day 3	Day 4	Day 5	Day 6	Day 7	Day 8	Day 9	Day 10 ¹	Day 11		
Admit to clinic	X																		
Discharge from clinic																		X	
Brief physical examination	X																X		A brief physical examination will include, at a minimum, assessments of the skin, lungs, cardiovascular system, and abdomen (liver and spleen).
Vital sign measurements	X	X		X	X	X	X	X	X	X	X	X	X	X	X	X	X	X	
12-Lead ECG	X	D1 and D5		D1 and D5			X			X	X		X				X		All ECGs in Period 1-3 will be pre-dose, post-dose at 2 hours, and post-dose at 4 hours. The predose ECGs on Day 1 of both Period 1 and Period 2 will be taken in triplicate.
Drug, alcohol, and cotinine screen	X																		See Appendix 2 for specific tests to be performed.
Laboratory assessments (hematology, chemistry, urinalysis)	X		D9			X				X			X				X		See Appendix 2 for specific tests to be performed.
Pregnancy test	X																X		
Columbia Suicide Severity Rating Scale				D1									X						
Genetic sample	X																		

Procedure	Period 1		W	Period 2			Period 3							Follow-up				Notes

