7.1.2. QTc Stopping Criteria

The *same* Fridericia QT correction formula (QTcF) correction formula *must* be used for *each individual participant* to determine eligibility for and discontinuation from the study. This formula may not be changed or substituted once the participant has been enrolled.

- The Baseline QTcF should be based on averaged QTcF values of triplicate electrocardiograms obtained over a brief (e.g., 5-10 minute) recording period from the Day 1 pre-dose ECG.
- A randomized participant that develops an on-treatment QTcF >500 msec or an increase from baseline QTcF >60 msec should have two repeat unscheduled ECG's within 10 minutes. Using these triplicate ECGs, if the average QTcF >500 msec or an increase from baseline QTcF >60 msec, the participant will be withdrawn from the study. Finally, this participant should have repeated unscheduled ECGs until their QTcF measurement returns to their original averaged QTcF value at Day 1 pre-dose.

See the SoA (Section [1.3](#)) for data to be collected at the time of treatment discontinuation and follow-up and for any further evaluations that need to be completed.

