	Grade 1	Grade 2	Grade 3	Grade 4	
Glucose/Glycosuria (random collection tested by dipstick)	Trace to 1+ or ≤ 250 mg	2+ or > 250 to ≤ 500 mg	> 2+ or > 500 mg	NA	
Protein/Proteinuria (random collection tested by dipstick)	1+	2+	3+ or higher	NA	
Red Blood Cells (RBCs)/Hematuria (not to be reported based on dipstick findings or on blood believed to be of menstrual origin)	6 to < 10 RBCs per high power field	≥ 10 RBCs per high power field	Gross, with or without clots OR with RBC casts OR intervention indicated	Life-threatening consequences	

NA=not applicable

10.7. **Appendix 7: Values of Potential Clinical Importance**

10.7.1. **ECG**

ECG Parameter	Units	Potential Clinically Important Range		
		Lower	Upper	
Absolute				
		< 320[1]	> 450[1]	
Abaaluta OTa Intonual		> 450[2]	≤ 480 ²]	
Absolute QTc Interval	msec	> 480[2]	≤ 500 ^[2]	
		> 500[2]		
Absolute PR Interval	msec	< 120[1]	> 200[1]	
Absolute QRS Interval	msec	< 60[1]	> 120[1]	
Change from Baseline				
	msec	≤ 30 ^[2]		
Increase from Baseline QTc	msec	> 30[1]	≤ 60 ^[2]	
	msec	> 60[2]		

NOTES:

- Represent standard ECG values of potential clinical importance for HV studies.
 Represent further subdivisions of ECG values for analysis.

10.7.2. **Vital Signs**

Vital Sign Parameter	Units	Potential Clinically	Important Range
(Absolute)		Lower	Upper
Systolic Blood Pressure	mmHg	< 85	> 140
Diastolic Blood Pressure	mmHg	< 45	> 90
Heart Rate	bpm	< 40	> 100

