10.9.5. Safety Tables

Safety:	Safety: Tables						
No.	Population	IDSL / Example Shell	Title	Programming Notes	Deliverable		
Advers	e Events (AEs)						
2.1.	Safety	AE1CP	Summary of Adverse Events by System Organ Class and Preferred Term		SAC		
2.2.	Safety	AE1CP	Summary of Drug-Related Adverse Events by System Organ Class and Preferred Term		SAC		
2.3.	Safety	AE3	Summary of Common (>=5%) Adverse Events by Overall Frequency		SAC		
2.4.	Safety	AE15	Summary of Common (>=5%) Non-serious Adverse Events by System Organ Class and Preferred Term (Number of Subjects and Occurrences)		SAC		
2.5.	Safety	AE16	Summary of Serious Adverse Events by System Organ Class and Preferred Term (Number of Subjects and Occurrences)		SAC		
2.6.	Safety	AE5A	Summary of Adverse Events by System Organ Class and Preferred Term and Maximum Intensity		SAC		
Laborat	tory: Chemistry	/					
2.7.	Safety	LB1	Summary of Clinical Chemistry Changes from Baseline		SAC		
2.8.	Safety	LB16	Summary of Clinical Chemistry Results by Maximum Grade Increase Post-Baseline Relative to Baseline		SAC		
Laborat	tory: Hematolo	gy					
2.9.	Safety	LB1	Summary of Hematology Changes from Baseline		SAC		
2.10.	Safety	LB16	Summary of Hematology Results by Maximum Grade Increase Post-Baseline Relative to Baseline		SAC		

Safety:	Tables				
No.	Population	IDSL / Example Shell	Title	Programming Notes	Deliverable
Labora	tory: Urinalysis	S			•
2.11.	Safety	UR3	Summary of Urinalysis Dipstick Results		SAC
2.12.	Safety	LB1	Summary of Urine Concentration Changes from Baseline		SAC
2.13.	Safety	LB16	Summary of Urinalysis by Maximum Grade Increase Post- Baseline Relative to Baseline		SAC
ECG					
2.14.	Safety	EG1	Summary of ECG Findings		SAC
2.15.	Safety	EG2	Summary of ECG Changes from Baseline		SAC
2.16.	Safety	EG10	Summary of Maximum QTc Values Post-Baseline Relative to Baseline by Category		SAC
2.17.	Safety	EG11	Summary of Maximum Increase in QTc Values Post-Baseline Relative to Baseline by Category		SAC
Vital Si	gns				
2.18.	Safety	VS1	Summary of Vital Sign Changes from Baseline		SAC
C-SSR	S				
2.19.	Safety	CSSRS4	Listing of C-SSRS Suicidal Ideation and Behavior Data		SAC

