28.	Safety	EG4	Listing of All ECG Values for Subjects with Any Value of Potential Clinical Importance		SAC		
Vital Sig	gns						
29.	Safety	VS5	Listing of All Vital Signs of Potential Clinical Importance		SAC		
30.	Safety	VS5	Listing of All Vital Signs for Subjects with any Value of Potential Clinical Importance		SAC		

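### SAP 10.3.2 keeps unscheduled safety readings for worst-case values but gives out-of-window scheduled readings no such exception, so read literally a late reading could be left out of the maximum-QTc and maximum-grade tables

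*SAP*

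**What the plan says.** Two neighbouring rules in SAP 10.3.2 (Reporting Standards) deal with readings that are off schedule.

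- **Out of window.** "Visits outside the protocol defined time-windows (i.e. recorded as protocol deviations) will be included in listings but omitted from figures". The sentence then adds "summaries and statistical analyses (excluding statistical analyses of PK parameters" and ends there. Its qualifiers concern PK only: for PK concentrations, only the mean figures lose the reading, and the statistical analyses of PK parameters are exempt.
- **Unscheduled.** "Unscheduled visits will not be included in summary tables except for determining the worst-case values".

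The displays in question are in SAP 10.9.5. Table 2.17 is the "Summary of Maximum Increase in QTc Values Post-Baseline Relative to Baseline by Category". Table 2.16 does the same for maximum QTc values. Tables 2.8, 2.10 and 2.13 summarise the maximum grade increase for chemistry, hematology and urinalysis. SAP 10.7.1 splits the item "Increase from Baseline QTc" into up to 30, above 30 to 60, and above 60 msec.

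On timing, the note in the protocol's Schedule of Activities reads: "All ECGs in Period 1-3 will be pre-dose, post-dose at 2 hours, and post-dose at 4 hours". Neither document gives a tolerance around those times.

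**The concern.** The author of SAP 10.3.2 saw that a table of worst values needs an exception for off-schedule readings, but wrote it for one kind only. A programmer who follows the text could count an unscheduled ECG and drop a scheduled 4 h ECG taken at the same clock time and recorded as a timing deviation. No reason is given for treating them differently.

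There is a good reason to keep late readings out of a mean by time point, because they no longer represent that time. That reason does not apply to a maximum over the period. Protocol 2.3 names QTc prolongation as one of three major risks of GSK3640254, and protocol 2.2 and 2.3 describe the earlier first-in-human experience in worst-case terms (no value >500 msec, no increase >60 msec). Tables 2.16 and 2.17 are where a similar statement for this trial would be checked. What is at stake is the accuracy of a descriptive safety summary. No primary PK analysis is affected.

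**Working it through.** The plan states no figure on this point, so there is none to reproduce. The check is a comparison of text followed by simple counting.

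**1. The two rules side by side (SAP 10.3.2)**

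| Reading | Listings | Summary tables | Worst-case exception |
|---|---|---|---|
| Scheduled, out of window, recorded as deviation | kept | omitted | none stated for safety |
| Unscheduled | kept | omitted | yes |

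Tables 2.8, 2.10, 2.13, 2.16 and 2.17 are all titled as summaries, so the omission reaches them on a literal reading.

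**2. Direction of the effect.** With baseline held fixed, removing one post-baseline reading from a set can only lower the maximum or leave it unchanged. The rule cannot raise a worst-case value.

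**3. Scheduled post-baseline ECGs per participant.** Inputs are the Schedule of Activities and the Day 1 pre-dose baseline in SAP 5.2.

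- Period 1: Day 1 (2 h, 4 h) + Day 5 (pre-dose, 2 h, 4 h) = 2 + 3 = 5.
- Period 2: the same days, so 5.
- Period 3: Day 1 (2 h, 4 h) + Days 4, 5 and 7 (three each) = 2 + 9 = 11. Day 10 adds one to three, giving 12 to 14.

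**4. Weight of one dropped reading.** If the k readings are exchangeable, the chance that a given dropped reading was the participant's maximum is 1/k.

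- Periods 1 and 2: 1/5 = 20%.
- Period 3: 1/11 = 9.1%, 1/12 = 8.3%, 1/14 = 7.1%.

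Exchangeability is an assumption. With about 16 treated participants, one who changes category moves a row by 1/16 = 6.25 percentage points.

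**5. Illustration with assumed values.** Take Period 1 QTcF changes of 12, 18, 8 and 22 msec, plus 41 msec on a late Day 5 4 h ECG recorded as a deviation.

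- Rule read literally: maximum = 22 msec, category up to 30.
- Worst-case exception extended: maximum = 41 msec, category above 30 to 60.

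**6. What the repeat rule covers.** Under protocol 7.1.2, a participant with on-treatment QTcF >500 msec or a rise >60 msec "should have two repeat unscheduled ECG's within 10 minutes". Those repeats are unscheduled, so they count for worst case. A sustained severe value therefore still reaches Tables 2.16 and 2.17. A rise of >30 to 60 msec with QTcF at or below 500 msec triggers no repeats, and a severe first reading whose repeats are lower would be represented only by the lower ones.

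**7. What cannot be computed.** If each reading had probability p of being recorded out of window, independently of its value, the expected number of participants per treatment whose maximum is dropped would be about 16 × p. The documents give no p and no numeric window from which to judge it.

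**The case against.** The strongest reply has five parts.

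- **Silence is not a rule.** SAP 10.3.2 does not mention worst-case tables in the out-of-window sentence, and it applies the sponsor's reporting standards unless otherwise stated. Those standards are not in the documents and may handle late readings sensibly. This stands: the reach to the maximum tables is inferred from the missing exception.
- **The trigger may seldom or never be met.** The rule speaks of visits outside protocol-defined windows, yet no numeric window for safety readings is defined. Participants are confined from Day -1 to Day 11 of Period 3, and deviation handling sits in a separate plan (SAP 4.1). This also stands. It makes the frequency unknown and probably low, but it also leaves what is dropped to how a delay is coded.
- **Severe values are repeated.** This largely stands, as step 6 shows.
- **Nothing leaves the report.** Late values stay in listings, including the "Listing of All ECG Values for Subjects with Any Value of Potential Clinical Importance", and clinically significant ECG or laboratory abnormalities are adverse events. The impact of major timing deviations is also to be assessed as appropriate. This stands, with the limit that SAP 10.3.2 keeps participant listings out of the main body of the report and that an impact assessment does not put a value back in a table.
- **Other displays carry QTc.** The only QTcF display that SAP 8.3 itself describes is the figure of mean change, so the maximum tables should not be called the main summary. This stands.

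Two stronger readings are tempting. A reader might infer that a late ECG with a severe rise is certain to disappear. The documents do not support that, given the silence on worst-case tables, the counted repeats and the listings. A reader might also infer that, because Period 2 has a single scheduled laboratory sample (Day 7), one late draw removes the participant from the grade tables for GSK3640254 alone. The schedule sets laboratory tests by day without a clock time, so a later draw that day is not shown to breach any window.

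**Conclusion.** The point holds as a drafting gap of low severity. The text treats two kinds of off-schedule reading differently without a reason, and the difference can only lower a worst-case summary. The conclusion rests on a literal reading of SAP 10.3.2 and on a late reading actually being recorded as a window deviation.

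The practical exposure is narrow: mainly the >30 to 60 msec category in Table 2.17, and larger rises whose repeats fall back. The maximum-grade laboratory tables share the wording problem, but no concrete case of loss is shown there. Per dropped ECG, the share of a participant's scheduled post-baseline readings is 20% in Periods 1 and 2 and about 9% or less in Period 3. How often this would happen cannot be stated, and the confined setting suggests rarely.

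**What to change.** In SAP 10.3.2, limit the omission of out-of-window safety readings to by-time-point summaries and figures, leave the PK rules as they are, and add:

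*Out-of-window post-baseline safety assessments (ECG, vital signs, laboratory) will be included when determining worst-case values and any-visit-post-baseline rows, as for unscheduled visits.*

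It would also help to state, or to cite from the deviation plan, what counts as out of window for an ECG, so that the by-time-point omission is reproducible.

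The cost is one sentence in the SAP and one programming flag. No new data are needed and no PK analysis changes. If the sponsor's standards already keep late readings for worst case, the sentence only records existing practice.
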